17.3.2 Other Laboratory Parameters

All other parameters collected on the eCRF will be listed in dedicated listings presenting all corresponding collected data-fields on the eCRF.

- Coagulation: aPTT, prothrombin time INR
- Urinalysis: all urinalysis parameters
- Other parameters: such as immunology, soluble factor
- Pregnancy test
- Serology

17.4 Vital Signs

Summary of vital signs will be based on the SAF. The potentially clinically significant changes from baseline as below in vital signs will be derived and summarized with subject incidence and percentage during the on-treatment period:

- $\geq 10\%$ weight increase
- $\geq 10\%$ weight decreases
- ≤ 95 mmHg and decrease from baseline ≥ 20 mmHg in systolic blood pressure
- ≥ 160 mmHg and increased from baseline ≥ 20 mmHg in systolic blood pressure
- ≤ 45 mmHg and decrease from baseline ≥ 10 mmHg in diastolic blood pressure
- ≥ 110 mmHg and increased from baseline ≥ 10 mmHg in diastolic blood pressure
- ≤ 50 bpm and decrease from baseline ≥ 20 bpm in pulse rate
- ≥ 120 bpm and increase from baseline ≥ 20 bpm in pulse rate

Quantitative data will also be examined for trends using descriptive statistics (n, missing, mean, SD, median, Q1, Q3, minimum, and maximum) of actual values, absolute changes and percent changes from baseline to each visit based on visit windows specified in Section 11. This summarization will apply to weight, blood pressure, respiratory rate, pulse, and temperature assessed at baseline, post-baseline, discontinuation, end of treatment, and safety follow-up visits.

Data listing of all vital signs will be provided with all relevant information such as visit, assessment date, parameter, and results.

17.5 Other Safety or Tolerability Evaluations

The incidence and percentage of subjects with potentially clinically significant abnormalities (PCSA) for 12-lead ECG parameters will be summarized for scheduled visits during the on-treatment period based on the SAF. The PCSA criteria are provided in the Table 14.

Table 14 Potentially Clinically Significant Abnormalities Criteria for ECG

Test	Potentially Clinically Significant Abnormalities (PCSA) Criteria
Heart Rate (HR)	≤ 50 bpm and decrease from baseline ≥ 20 bpm ≥ 120 bpm and increased from baseline ≥ 20 bpm
PR Interval	≥ 220 ms and increase from baseline ≥ 20 ms
QRS	≥ 120 ms
QTcF, QTcB absolute	interval >450 - ≤ 480 ms interval >480 - ≤ 500 ms interval >500 ms
QTcF, QTcB change from baseline	Increase from baseline > 30 - ≤ 60 ms Increase from baseline > 60 ms

QT interval will be corrected based on Fridericia’s formula ($QTcF = QT / \sqrt[3]{RR}$) and RR=60/HR, Bazett’s formula ($QTcB = QT / \sqrt{RR}$) and RR=60/HR, and lineal regression, if possible. The correction be linear regression (QTcP) will be performed as:

- Fit a linear regression model $QT = a + b * RR$ to baseline QT and RR data of the SAF subjects.
- Use the estimated slope, \hat{b} , to correct QT
- Corrected QT will be computed as $QTcP = QT + \hat{b} * (1 - RR)$

Baseline QTcF/QTcB/QTcP will be derived from the visit that QT and HR are flagged as baseline. If there are multiple assessments at the same visit and time point, the average will be calculated for each parameter and used for the analysis.

Quantitative data will also be examined for trends using descriptive statistics (n, missing, mean, SD, median, Q1, Q3, minimum, and maximum) of actual values (with 95% CI of the mean), absolute changes from baseline (with 90% CI of the mean) to each visit based on visit windows specified in Section 11. This summarization will apply to heart rate, QRS interval, QT interval, PR interval, QTcB, and QTcF assessed at baseline, post-baseline, discontinuation, end of treatment, and/or safety follow-up visits.

Listings of 12-lead ECGs will be provided with all relevant information such as visit, date/time of assessment, parameter, and results.

The ECOG shift from baseline to highest on-treatment score will be summarized by cohort based on SAF analysis set. Missing category will be included and the number of subjects in each cohort will be used as the denominator.

ECOG performance status will also be presented in a data listing.

Data of subject status and survival follow-up will be provided in a listing.

18 Reporting Conventions

- Reporting will require placement of decimals, and this will depend on the raw data collected. Generally, mean and median should be displayed one more decimal place than the raw data and standard deviation should be displayed two more decimal place than the raw data. Percentages will be reported as one decimal place.
- The rounding will be performed to closest integer / first decimal using the common mid-point between the two consecutive values. E.g. 5.1 to 5.4 will be rounded to an integer of 5, and 5.5 to 5.9 will be rounded to an integer of 6.
- The following conversion factors will be used to convert days to months or years, where applicable: 1 month = 30.4375 days and 1 year = 365.25 days.
- Data listings will be sorted by dose level, subject identifier, visit or date (if applicable), or parameters, as appropriate.

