17.5 Other Safety or Tolerability Evaluations

The incidence and percentage of subjects with potentially clinically significant abnormalities (PCSA) for 12-lead ECG parameters will be summarized during the on-treatment period based on SAF analysis set. The PCSA criteria are provided in the Table 7.

Table 7 Potentially Clinically Significant Abnormalities Criteria for ECG

Test	Potentially Clinically Significant Abnormalities (PCSA) Criteria
Heart Rate (HR)	≤ 50 bpm and decrease from baseline ≥ 20 bpm ≥ 120 bpm and increased from baseline ≥ 20 bpm
PR Interval	≥ 220 ms and increase from baseline ≥ 20 ms
QRS	≥ 120 ms
QTcF, QTcB absolute	interval $>450 - \leq 480$ ms interval $>480 - \leq 500$ ms interval >500 ms
QTcF, QTcB change from baseline	Increase from baseline $> 30 - \leq 60$ ms Increase from baseline > 60 ms

QT will be corrected based on Fridericia's formula ($QTcF = QT / \sqrt[3]{RR}$) and $RR = 60/HR$, and Bazett's formula ($QTcB = QT / \sqrt{RR}$) and $RR = 60/HR$, if possible. Baseline QTcF/QTcB will be derived from the visit that QT and HR are flagged as baseline. If there are multiple assessments at the same visit and time point, the average will be calculated for each parameter and used for the analysis. Quantitative data will also be examined for trends using descriptive statistics (n, missing, mean, SD, median, Q1, Q3, minimum, and maximum) of actual values (with 95% CI of the mean), absolute changes from baseline (with 90% CI of the mean) to each visit based on visit windows

specified in [Section 11](#). This summarization will apply to heart rate, QRS interval, QT interval, PR interval, QTcB, and QTcF assessed at baseline, post-baseline, discontinuation, end of treatment, and/or safety follow-up visits.

Listings of 12-lead ECGs will be provided with all relevant information such as visit, date/time of assessment, parameter, and results.

The ECOG shift from baseline to highest on-treatment score will be summarized by dose level and overall based on SAF analysis set. Missing category will be included and the number of subjects in each dose level will be used as the denominator.

ECOG performance status will also be presented in a data listing.

18 Reporting Conventions

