- On-treatment period will be defined as the time from the first dose of study treatment to min(last dose date + 30 days, earliest date of subsequent anti-cancer drug therapy – 1 day). If the earliest date of subsequent anti-cancer drug therapy is a partial date and only day is missing, it will be imputed as the last day of the month. If both day and month are missing, no imputation should be performed. The imputed date will be used for defining on-treatment period as well as confirming immune-related progressive disease (irPD).
- All statistical analyses will be performed using SAS® Version 9.1.3 or higher.
- There will be no difference between scheduled and un-scheduled visits except for by-visit analysis of safety analyses and baseline derivation.
- The assignments of visit windows are described in Table 5 for the purpose of by-visit analyses of safety data:
 - Baseline will be derived as described above.
 - No visit windowing will be performed at discontinuation, end of treatment, or safety follow-up visits for laboratory, vital sign, and ECG data, and 2hr post dose assessment on Week 1 Day 1 for ECG data. Instead, the earliest non-missing observation among the unscheduled or scheduled assessments for each visit (discontinuation, end of treatment, or safety follow-up) will be used for the analysis. For 2hr post dose assessment on Week 1 Day 1 ECG data, the earliest non-missing observation on Week 1 Day 1 will be used for the analysis.

- Scheduled and unscheduled assessments are included for visit windowing. Assessments on or after re-initiation of treatment are not be included for visit windowing.
- If there are multiple assessments for any specified visit and some of them are from scheduled visits, the assessment from scheduled visit with the closest distance to the planned study day will be used for analysis.
- If there are multiple assessments for any specified visit and none of them are from scheduled visits, the assessment with the closest distance to the planned study day will be used for analysis.
- If there are two or more unscheduled assessments with same distance to the planned study day such as (-1/+1 day), the assessment prior to the planned study day such as -1 day will be used for windowing.

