- There is no difference for visit windowing between tests from core serum chemistry panel and tests from full serum chemistry panel. Some subjects had non-core serum chemistry tests assessed at the scheduled visits only intended for core serum chemistry. Multiple protocol amendments are also taken into the consideration, as the full serum chemistry and hematology panels were assessed weekly until week 7 and bi-weekly thereafter prior to the approval of Protocol Amendment 7.
- For ECG assessment associated with study treatment dose, only assessments where time point (prior to infusion or 2 hr after infusion) are not missing will be considered for the analysis.

Table 5 Visit Window Definition for Safety Assessment

Assigned Study Day (Inclusive)		Planned Study Day (AWTARGET)	Analysis Visit (N) (AVISITN)	Analysis Visit (AVISIT)	Assessment
From (AWLO)	To (AWHI)				
~	1		1	Baseline	Lab, Vital Sign, ECG
1	1	1	2	Week 1 Day 1*	ECG
5	11	8	3	Week 2 Day 5-11	Lab, Vital Sign
12	18	15	4	Week 3 Day 12-18	Lab, Vital Sign
5	18	15	4	Week 3 Day 5-18	ECG
19	25	22	5	Week 4 Day 19-25	Lab, Vital Sign
19	25	22	5	Week 4 Day 19-25	ECG
26	32	29	6	Week 5 Day 26-32	Lab, Vital Sign
26	36	29	6	Week 5 Day 26-36	ECG
33	39	36	7	Week 6 Day 33-39	Lab, Vital Sign

40	50	43	8	Week 7 Day 40-50	Lab, Vital Sign
37	50	43	8	Week 7 Day 37-50	ECG
51	64	57	10	Week 9 Day 51-64	Lab, Vital Sign, ECG
65	78	71	12	Week 11 Day 65-78	Lab, Vital Sign, ECG
79	92	85	14	Week 13 Day 79-92	Lab, Vital Sign
79	106	85	14	Week 13 Day 79-106	ECG
93	106	99	16	Week 15 Day 93-106	Lab, Vital Sign
107	120	113	18	Week 17 Day 107-120	Lab, Vital Sign
121	134	127	20	Week 19 Day 121-134	Lab, Vital Sign
107	148	127	20	Week 19 Day 107-148	ECG
135	148	141	22	Week 21 Day 135-148	Lab, Vital Sign
149	162	155	24	Week 23 Day 149-162	Lab, Vital Sign
163	176	169	26	Week 25 Day 163-176	Lab, Vital Sign
149	190	169	26	Week 25 Day 149-190	ECG
177	190	183	28	Week 27 Day 177-190	Lab, Vital Sign
191	204	197	30	Week 29 Day 191-204	Lab, Vital Sign
205	218	211	32	Week 31 Day 205-218	Lab, Vital Sign
191	232	211	32	Week 31 Day 191-232	ECG

* only applies to 2 hr post dose, AWLO = Analysis Window Beginning Timepoint, AWHI = Analysis Window Ending Timepoint, AWTARGET = Analysis Window Target, AVISIT = Analysis Visit, AVISITN = Analysis Visit (N).

- Presentation of continuous and qualitative variables:

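### Expansion SAP 17.5 counts ECG abnormalities at scheduled visits only, against the Section 11 rule, so unscheduled on-treatment ECGs drop out of that incidence table

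*SAP*

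**What the plan says.** Expansion SAP 17.5 plans a table of the number and percentage of subjects with PCSA that "for 12-lead ECG parameters will be summarized for scheduled visits during the" on-treatment period, in the safety set. The criteria, in Table 14, cover heart rate, PR, QRS, and absolute values and changes of QTcF and QTcB. The top QTc categories are above 500 ms and an increase of more than 60 ms.

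The dose-escalation SAP, also in 17.5, has the same table with the same criteria (its Table 7), but there the incidence "for 12-lead ECG parameters will be summarized during the on-treatment period based on SAF analysis set".

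The general rule is in Section 11 of the expansion SAP: "There will be no difference between scheduled and un-scheduled visits except for by-visit analysis of safety analyses and baseline derivation". Two further Section 11 rules bear on ECGs. For by-visit summaries, "Scheduled and unscheduled assessments are included for visit windowing", with a scheduled assessment preferred when a window holds both kinds. For ECGs tied to a dose, "only assessments where time point (prior to infusion or 2 hr after infusion) are not missing will be considered for the analysis".

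**The concern.** A PCSA table is the plan's numeric statement of how many subjects ever crossed a cardiac safety threshold while on treatment. Restricting the source ECGs to scheduled visits discards tracings that belong to that period. Scheduled ECGs become sparser over time: protocol 7.1.2.2 has them every 2 weeks at first and every 6 weeks later, each with a pre-infusion and a 2-hour post-infusion tracing. An abnormal value recorded between those visits would be missing from the count, and the SAP gives no reason for leaving it out.

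The interim report is also affected. Both phases use a 20 November 2015 cut-off (dose-escalation SAP Section 9, expansion SAP 8.2), and expansion SAP Section 9 refers to a joint interim escalation and expansion report. A reader would see two tables with the same criteria that admit different ECGs.

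**Working it through.** There is no planned figure to reproduce. The check is a comparison of texts, followed by the direction of the effect.

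**Which records each rule admits**

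| Place | Output or rule | Records admitted |
|---|---|---|
| Expansion SAP 17.5 | ECG PCSA incidence | On-treatment, scheduled visits only |
| Dose-escalation SAP 17.5 | Same table, same criteria | On-treatment, no visit limit |
| Expansion SAP 17.4 | Vital-sign abnormality incidence | "derived and summarized with subject incidence and percentage during the on-treatment period", no visit limit |
| Expansion SAP 17.3.1 | Laboratory worst grade | Highest on-treatment grade, no visit limit |
| Expansion SAP Section 11 | General rule | Both kinds alike, outside by-visit safety analyses and baseline |

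The first row stands alone. Pulse rate in 17.4 and ECG heart rate in 17.5 use identical thresholds (50 bpm or below with a fall of at least 20; 120 bpm or above with a rise of at least 20) but follow different inclusion rules.

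**Does the by-visit exception cover this table?** Section 17.5 describes the by-visit ECG summary in a separate paragraph: descriptive statistics, with confidence intervals for the mean, by windowed visit. The PCSA sentence describes the incidence and percentage of subjects over the on-treatment period. Read naturally, it is not a by-visit analysis, so the general rule should govern it and 17.5 contradicts that rule.

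**Direction of the effect.** For subject i, let S be the set of scheduled on-treatment ECGs and A the set of all on-treatment ECGs. S is contained in A, so max(S) ≤ max(A) for QTcF. Every subject with max(S) above 500 ms also has max(A) above 500 ms, and the reverse need not hold. The subjects missed are those with max(S) ≤ 500 ms and max(A) > 500 ms. The denominator is the safety set either way, with missing values included under Section 11, so the percentage can only be too low. The same argument applies to an increase above 60 ms and to the heart-rate, PR and QRS criteria, which have a single threshold and no bands.

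It does not apply to the lower QTc bands. If each subject is classified once, by worst value, a subject whose worst scheduled value lies in the band above 450 to 480 ms, but who has an unscheduled value above 500 ms, is counted in the lower band under 17.5. That band could be overstated.

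**Size.** The undercount in any top category lies between 0 and U, where U is the number of subjects with at least one unscheduled on-treatment ECG. Neither document gives U.

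**Whether other outputs recover the count.**
- By-visit tables: an unscheduled ECG enters only if its window has no scheduled one, and the ECG windows in Table 5 end at Day 232.
- ECG listing: shows the tracing but gives no incidence.
- Adverse event tables: under protocol 7.4.1.1, an abnormal ECG finding is reported only if it is symptomatic, leads to discontinuation or is judged medically important.

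**The case against.** The strongest counter-argument is that little is lost. A symptomatic or medically important ECG finding should be reported as an adverse event and so reach the tables by system organ class, preferred term and grade. An adverse event that mandates stopping treatment triggers a discontinuation visit within 7 days, with its own 12-lead ECG (protocol 7.1.3). That is a protocol visit and can count if it falls in the on-treatment period. The end-of-treatment visit at 28 days also lies inside the window of last dose plus 30 days, unless new anticancer drug therapy ends the window sooner. ECG is not a named endpoint, and the analysis is descriptive. All of this stands and limits the consequence. It does not supply a numeric incidence of threshold crossings, which is what the table is for.

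It can also be argued that the phrase only means incidence shown by scheduled visit, which Section 11 exempts. The wording leaves some room for this, but the separate by-visit paragraph in 17.5 makes the reading strained. Even on that reading, a scheduled ECG displaces an unscheduled one in its window.

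A reader might infer that the omitted ECGs are mainly symptom-driven, and that cardiac events therefore disappear from the report. The documents do not support this. They do not say why unscheduled ECGs are taken, the cardiac rows of protocol Table 6.2 do not mention an ECG, and the listing and adverse event routes remain. A reader might also infer that a planned comparison with dose escalation is spoiled. Neither SAP plans one for ECG abnormalities.

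**Conclusion.** The point holds as an internal inconsistency with a known direction. Section 17.5 of the expansion SAP leaves unscheduled on-treatment ECGs out of the PCSA incidence, contrary to Section 11 and out of line with the three comparable tables. Incidence in the most extreme categories can be understated and cannot be overstated. The size is unknown and could be zero.

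This rests on three assumptions: the specific sentence in 17.5 governs the programming; the denominator is the safety set; and an unscheduled tracing counts as its own visit, so that the 17.5 rule of averaging repeats at one visit and time point does not merge it with a scheduled one. The primary endpoint is not affected. Because the correction is nearly free and removes a downward bias from a safety table, it should be made.

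**What to change.** In expansion SAP 17.5:

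1. Delete *for scheduled visits*, so that all on-treatment ECGs, scheduled and unscheduled, enter the PCSA table.
2. State that each subject is classified by the most extreme on-treatment value for each parameter. The SAP does not now say how repeated values are reduced.
3. State that the Section 11 filter on pre-infusion or 2-hour time points does not apply to this table. It sits among the visit-windowing rules, but if a programmer applied it here, an unscheduled ECG without a recorded time point could still drop out after the deletion.

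Leave the Section 11 windowing rules for the by-visit descriptive tables as they are; they already admit unscheduled ECGs and prefer scheduled ones. The cost is one deleted phrase, two added sentences and one program filter. No new data are needed.

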18.1 Date of Last Contact

The date of last contact will be derived for patients not known to have died at the analysis cut-off using the latest complete date among the following:

- All patient assessment dates (blood draws (laboratory, PK), vital signs, performance status, ECG, tumor assessments)
- Start and end dates of anti-cancer therapies administered after study treatment discontinuation.
- AE start and end dates
- Last date of contact collected on the 'Subject Status/Survival Follow-up' eCRF (do not use date of survival follow-up assessment unless status is 'alive')
- Study treatment start and end dates
- Date of discontinuation on disposition eCRF pages (do not use if reason for discontinuation is lost to follow-up).

Only dates associated with actual examinations of the patient will be used in the derivation. Dates associated with a technical operation unrelated to patient status such as the date a blood sample was processed will not be used. Assessment dates after the cut-off date will not be applied to derive the last contact date.

18.2 Incomplete Dates

Missing or partial start dates for adverse events will be imputed as following:

- When the start Date of the AE is missing (but Month & Year is available), then the AE date will be imputed to the "1st Date of the reported Month" (e.g. if reported date is --/JAN/09, imputed date will be 01/JAN/09). If the reported AE Month = the Month of the First Dosing date, then the AE date will be imputed to the "1st Dosing date" (e.g. if AE reported date is --/JAN/09, and the First doing date is 13/JAN/09, then the AE imputed date will be 13/JAN/09).

- When the Date & the Month of the AE is missing (but Year is available), then the AE date will be imputed to the "1st Date of the 1st Month of the reported Year" (e.g. if reported date is --/--/09, imputed date will be 01/JAN/09). If the reported AE Year = the Year of the First Dosing date, then the AE date & month will be imputed to the "1st Dosing date" (e.g. if AE reported date is --/--/09, and the First dosing date is 13/APR/09, then the AE imputed date will be 13/APR/09).
- When the date is completely missing, no imputation will be performed and the AE will be considered as treatment emergent, unless there is rationale to clarify otherwise, eg. AE stop date is prior to the first dose date.

Missing or partial dates for concomitant medications will be imputed as following:

- If the start day of medication is missing, it will be imputed to the first day of the month; if the stop day is missing, it will be imputed to the last day of the month. If both day and month are missing, the start date will be imputed as the first day of the year and stop date will be imputed as the last day of the year. If the start or stop date is completely missing, no imputation will be performed and the determination of pre-medication or post-medication will be based on non-missing stop or start date, respectively; otherwise, the medication will be considered as concomitant.

Missing or partial dates for disease history (initial diagnosis date, first occurrence of metastatic or locally advanced disease, date of last progression of disease) will be imputed as following:

- If the day is missing, it will be imputed to the 15th day of the month; if both day and month are missing and the year is prior to the year of the first study treatment, the month and day will be imputed as July 1st; if both day and month are missing and the year is same as the year of the first study treatment, the month and day will be imputed as January 1st. If the date is completely missing, no imputation will be performed.

Partial dates for prior anti-cancer drug therapies will be imputed as following:

- If the day is missing, it will be imputed to the first day of the month; if both day and month are missing, no imputation will be performed.

Missing or partial death dates will be imputed based on the last contact date:

- If the date is missing it will be imputed as day after date of last contact from the CRF survival page
- If the day or month is missing, death will be imputed to the maximum of the full (non-imputed) day after the date of last contact and the following:
 - Missing day: 1st day of the month and year of death
 - Missing day and month: January 1st of the year of death

If the day is missing from the date of last contact it will be imputed to 1st day of the month and year of last contact only if derived from the survival page.

No other dates will be imputed.

19 **References**

1. Eisenhauer EA. New response evaluation criteria in solid tumours: Revised RECIST guideline (version 1.1). *Eur J Cancer* 2009;45:228-47.
2. Wolchok et al. Guidelines for the evaluation of immune therapy activity in solid tumors: immune-related response criteria. *Clin Cancer Res* 2009;15(23):7412-20.

20

Appendices

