7.4.1.3 Definition of the Adverse Event Reporting Period

The AE reporting period for safety surveillance begins when the subject is included into the trial (date of first signature of informed consent) and continues through the trial's End-of-Treatment visit, 28 days after last trial drug administration. After the End-of-Treatment visit only treatment-related AEs have to be documented through the post-treatment safety follow-up period, defined as 10 weeks after the last trial drug administration.

Any SAE suspected to be related to the trial treatment must be reported whenever it occurs, irrespective of the time elapsed since the last administration.

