- Analysis results will be summarized by cohort(s) and/or pooled across cohorts, depending upon the purpose of the reporting. Primary analysis for a cohort will include data summarized by that cohort. Final analysis will include data from all the expansion cohorts.
- Analysis of primary gastric and GEJ cancer cohort will be primarily stratified by the status of disease progression after first line chemotherapy.

- Data collected after re-initiation of treatment will not be included for safety and efficacy analyses except for PK, overall survival, and disposition.
- All data will be evaluated as observed, and no imputation method for missing values will be used, unless otherwise specified.
- Duration will be calculated as stop date – start date + 1, unless otherwise specified.
- The time since an event (e.g. time since first diagnosis, time since last dose) will be calculated as reference date minus date of event.
- The first day (Day 1) of study treatment is defined as the day of the first administration of avelumab, unless otherwise stated. The last dose date of study treatment is defined as the day of the last administration of avelumab, prior to the re-initiation of study treatment if applicable.
- Baseline is defined as the last non-missing observation prior to the administration of first dose of study treatment. Additionally, baseline for HR and QT/corrected QT (QTc) assessments will be derived from the visit where both HR and QT are not missing. If duplicate or triplicate ECGs are collected, baseline for each ECG measurement is the average of the pre-dose replicate measurements on the baseline day. QT interval correction based Fridericia's or Bazett's formula (QTcF/QTcB) will be derived based on HR and QT. The average of the replicate measurements should be determined after the derivation of the individual parameter at each time point.
- If the laboratory assessments are not done for scheduled visit but they are available for unscheduled visit on Day 1 from a different laboratory, the unscheduled visit will be included for the derivation of baseline; if there are multiple non-missing assessments on Day 1, the assessment from scheduled visit will be used for the derivation of baseline.

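### Partial AE start dates are moved to the first dose date even when a known stop date shows that the event ended before treatment

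*SAP*

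**What the plan says.** Section 18.2 of the expansion SAP treats incomplete AE start dates in three bullets.

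- **Day missing.** The start goes to the first of the reported month, with one exception: "If the reported AE Month = the Month of the First Dosing date, then the AE date will be imputed to the" first dosing date. The SAP's own example ends: "First doing date is 13/JAN/09, then the AE imputed date will be 13/JAN/09".
- **Day and month missing.** The start goes to 1 January, again with an exception: "If the reported AE Year = the Year of the First Dosing date, then the AE date & month will be imputed to the" first dosing date.
- **Whole date missing.** "When the date is completely missing, no imputation will be performed and the AE will be considered as treatment emergent", unless there is reason to decide otherwise. The reason offered is that the "AE stop date is prior to the first dose date".

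Section 18.1 of the dose-escalation SAP has the same three bullets.

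Three other provisions matter. Protocol Section 7.4.1.3 states: "The AE reporting period for safety surveillance begins when the subject is included into the trial (date of first signature of informed consent"), so pre-dose events enter the database. In both SAPs the on-treatment period starts at first dose (Section 11), and an AE is treatment-emergent if its onset or worsening falls in that period (Section 17.1). Section 11 also fixes the arithmetic: "Duration will be calculated as stop date" minus start date plus 1, unless otherwise specified.

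For disease-history dates, a later paragraph of the same sections says: "If the day is missing, it will be imputed to the 15th day of the month".

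**The concern.** The first two bullets can contradict a date that the site has reported. If the stop date is complete and earlier than first dose, the start cannot be the first dose date. The rule assigns it anyway, and TEAE status then follows from the imputed onset.

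The ordering of the safeguards suggests an oversight. The stop date may overrule the default when nothing is known about the start, but it is not consulted when the month or year is known.

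Number, severity and duration of TEAEs form a secondary endpoint in both SAPs. What is at stake is that some screening-period events could be counted in the TEAE incidence tables, and that impossible durations could appear where AE duration is listed.

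**Working it through.** **Inputs.** The imputation rules come from expansion SAP 18.2 and escalation SAP 18.1. The duration formula and the on-treatment period come from Section 11 of each SAP. The 18-day screening window is from Protocol 7.1.1. The expansion schedule in Appendix I heads its pre-treatment column Day -28 (washout) / -18 (screening).

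**Step 1: reproduce the SAP's own examples.** Applied literally, --/JAN/09 with first dose 13/JAN/09 gives 13/JAN/09, and --/--/09 with first dose 13/APR/09 gives 13/APR/09. Both match the SAP.

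**Step 2: add a complete stop date before first dose.** Duration = stop - imputed start + 1.

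| Reported start | First dose = imputed start | Stop | Duration (days) |
|---|---|---|---|
| --/JAN/09 | 13/JAN/09 | 05/JAN/09 | 5 - 13 + 1 = -7 |
| --/JAN/09 | 13/JAN/09 | 10/JAN/09 | 10 - 13 + 1 = -2 |
| --/JAN/09 | 13/JAN/09 | 12/JAN/09 | 12 - 13 + 1 = 0 |
| --/--/09 | 13/APR/09 | 30/MAR/09 | -14 + 1 = -13 |
| --/--/09 | 13/APR/09 | 10/APR/09 | 10 - 13 + 1 = -2 |

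All five events ended before treatment, and all five are classed as treatment-emergent because the imputed onset is the first dose date. The duration is 0 when the event stopped one day before dosing, and negative when it stopped two or more days before. Every stop date here lies within 18 days of first dose, so each event could fall inside the AE reporting period.

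**Step 3: how often would a pre-dose day meet the month or year condition?** This needs an assumption. With first-dose dates spread evenly over a year, about 69% of the days in an 18-day pre-dose window fall in the first-dose month and about 97% in the first-dose year. With a 28-day window the figures are about 52% and 96%. So the condition is usually met once an event has a partial start and a pre-dose stop. These figures do not say how many such events exist.

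**Step 4: look for a repair elsewhere.** The stop-date exception is attached only to completely missing start dates. The TEAE definition uses onset or worsening, not the stop date. The duration formula has no floor. No other provision corrects the two partial-date bullets.

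**Step 5: disease history.** Time since last progression is (first dose date - progression date) / 30.4375 months (Section 13.3 of each SAP). For a progression reported with the day missing in March and first dose on 10 March, the imputed date is 15 March and the result is (10 - 15) / 30.4375 = -0.16 months. The worst case is a first dose on the 1st: the imputed date falls 14 days after dosing, and 14 / 30.4375 = 0.46 months.

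**The case against.** The best case for the SAPs is that moving an uncertain start to the first dose date is deliberately conservative, because it counts doubtful events as treatment-emergent. The affected records are also rare. Each needs an AE arising between consent and first dose, a partial start date, and a complete stop date before dosing. Sites are asked for onset and resolution dates (Protocol 7.4.1.2), and quality control precedes database lock (Protocol 10.1).

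The point on rarity stands. The conservatism argument holds while the timing is unknown, but not once the stop date settles it.

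A reader might also infer larger consequences, which the documents do not support:

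- **Events from months earlier.** The year-only rule might seem to draw in AEs long past. AE reporting starts at consent, and the pre-treatment window is 18 to 28 days, so an event that ended well before that window is not a reportable AE.
- **A biased duration estimate.** Neither SAP plans a summary statistic or test of AE duration. Duration is named as an item in one expansion listing (Section 17.1.1), where a negative value would stand beside the stop date.
- **False infusion-related reactions.** A pre-dose hypersensitivity term might seem able to become one. The definitions also require onset during or after the infusion, not before dosing (expansion SAP 17.1.4 and Appendix II; escalation SAP 17.1), and an imputed calendar date does not establish that.
- **An effect on the MTD.** The dose-limiting toxicities that determine it are confirmed by the safety monitoring committee (escalation SAP 16.1), not derived from imputed dates.

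**Conclusion.** The point holds in a limited form. In both SAPs, an AE with a partial start date matching the first-dose month (or year, if the month is missing) and a known stop date before first dose is wrongly classed as a TEAE, with a zero or negative duration. This follows from the stated rules and rests on no assumption beyond the existence of such a record, which the reporting period allows.

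The documents do not give the number of such records. It is probably small, so the effect on TEAE counts cannot be quantified. The consequences are confined to TEAE incidence counts and the listed AE duration.

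The disease-history rule is a separate and smaller matter. It involves no stop date and no safety endpoint. The imputed date can fall at most 14 days after first dose, in a descriptive baseline variable, and only when the event falls in the first-dose month and dosing is before the 15th. The year-only branch is already guarded, because it uses 1 January when the year matches that of first treatment.

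**What to change.** In expansion SAP 18.2 and escalation SAP 18.1, carry the third bullet's exception into the two partial-date bullets. If the AE stop date is before the first dose date, the event is not treatment-emergent and its start is not moved to the first dose date. The start is instead imputed no later than the stop date and, where the reported parts allow, no earlier than informed consent.

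The consent limit matters. For --/--/09 with stop 30/MAR/09, simply taking the earliest possible date would give 01/JAN/09 and a duration of 31 + 28 + 30 = 89 days, beginning long before AE reporting could have started.

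In the disease-history paragraph of both SAPs, add that a date imputed to the 15th may not fall after the first dose date.

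The cost is one clause per rule and a small program change. Records whose timing remains ambiguous stay treatment-emergent, as now.
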